## Methods.

### Design:

This is a proof-of-concept, prospective, randomized clinical trial for safety of TheraGauze-tobramycin in adult subjects who present to Emergency Department settings for care of skin abscess requiring incision and drainage. A control, standard of care, arm is included to provide some data with respect to the side effect profile of current furunculosis management for comparison.

Two arms are proposed for this study:

1. Incision + TheraGauze+tobramycin packing (no systemic antibiotics)
2. Incision + standard iodoform wick or plain cotton wick packing ( $\pm$  p.o. antibiotics)

Anti-microbial TheraGauze (saturated with tobramycin ophthalmic solution at 3 mg/ml) will be packed into the drained wounds of the subjects in the study arm. The control arm will receive current standard of care wound packing with a choice of iodoform wick or plain cotton wick, based on the preference of the ED physician. After packing, the wound excess TheraGauze or wick will be cut away. The ED physicians have the option to prescribe an oral antibiotic or not,

according to their preference. The following oral antibiotic choices are available for subjects in the control arm only:

- Bactrim (TMP/SMX)
- Vibramycin (doxycycline)
- Cleocin (clindamycin)

Antibiotics will be purchased by subjects from their local pharmacy.

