- Currently taking or has taken oral or injection steroid medication (e.g. prednisone or Medrol Dosepak) in the past 30 (thirty) days

- Injection medications (Remicade, Humira, Cimzia, Simponi) other than vitamin (B6)
- Currently taking or has taken immune suppressing medications (e.g. methotrexate, Prograf, CellCept, Rapamune) in the past 30 (thirty) days
- Currently taking or has taken medications to treat cancer in the past 30 (thirty) days
- Subject is currently participating or has participated within the last two months in any study of an investigational drug or device.

*Recruitment and Retention:*

Subjects who present to Emergency Department setting for care of skin abscess requiring incision and drainage will be approached by on-site Study Coordinators for enrollment. The study coordinators and physician investigators are trained in obtaining informed consent. The potential subjects will be able to discuss participation with any family-member present, but due to the need for prompt treatment, the subject will need to make a decision regarding participate at the time of the Emergency Room visit. Upon meeting eligibility criteria and willingness to participate, subjects/LARs will provide informed consent. Complete demographic information to include residential and telephone contact information will be obtained. Prior relevant medical history and usual primary care contact information will also be collected. A medical information release will be obtained from the subject so that outcomes data can be collected related to additional unscheduled visits or adverse events cared for outside the emergency department setting.

*Women and minority participation:*

Adults up to 65 years of age will be enrolled regardless of gender and minority status as long as they are fluent in English.

*Randomization:*

A study subject identification number will be assigned. Subjects will then be sequentially randomized to one of two treatment arms upon enrollment in a 2:1 ratio, using a prepared list. Each subject's name will be recorded on the list next to his/her assigned subject number and randomization. For example, the first subject enrolled will be randomized to Treatment 1; the next enrolled subjects will be enrolled to Treatment 1; the third subject to Treatment 2. The fourth subject will be randomized to Treatment 1 and so on.

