    - Cleocin (clindamycin)

Phone Follow up Contact Day 2 (+2)

Return visit reminder and wound status follow up performed by Sentara Study Coordinator.

- Questions
  - Fever since leaving ED? (y/n, record temp if taken)
  - If prescribed, was antibiotic prescription filled (y/n)
  - If prescribed, has antibiotic been taken (y/n, # doses)
  - If antibiotics taken, were any side-effects noted (y/n, list)
  - Increased or decreased pain (y/n, increased/decreased)
  - Increased or decreased size of redness (y/n, increased/decreased)
  - Any new symptoms? (y/n, list) Specific questions will include: presence of rash, loose stool, nausea, vomiting, abdominal discomfort, headache, dizziness, drowsiness, thrush, as well as any change in local signs or symptoms including pain and redness, new skin lesions, enlarged lymph nodes, and sore or white spots in the mouth.

Visit 2 - Day 3 -1/+2: (ED)

Subjects' wound status will be evaluated. The following information will be collected and recorded on a hard copy Case Report Form at this visit:

- Questions about infection
  - Infection overall (better/same/worse)
  - Fever > 38°C at home since incision? (y/n)
  - Persistent discharge (y/n)
  - Pain (increased/same/decreased/resolved)
  - Medical evaluation between day 1 and day 3 visit (y/n)
  - New lesions (y/n)
  - Was an p.o. antibiotic prescribed (y/n)
    - If yes, was the prescription filled (y/n)
    - How many doses have been taken so far? (##)
  - Any diarrhea? (y/n)
  - Any nausea or vomiting? (y/n)
  - Any abdominal discomfort? (y/n)
  - Any new rash? (y/n)
  - Any other new symptoms including headache, dizziness, drowsiness, thrush, as well as any change in local symptoms.
  -
- Bacterial burden in wound bed – Wound culture performed using quantitative methods for culturing wound base (Gardner, Frantz et al. 2006). Cultures taken to [name] lab for quantitation, swab may be stored at 4°C, if obtained after business hours.
  - Quantitation of bacteria present (colony counts performed in [name] lab)
  - Speciation of bacteria present (CHKD clinical microbiology laboratory using CLSI standards)
  - Antibiotic susceptibility testing of bacteria present (CHKD clinical microbiology laboratory using CLSI standards)
- Wound assessment
  - Fever > 38°C in ED? (y/n, record temp)
  - Packing present (y/n)
  - Erythema at widest diameter (mm)

- Abscess induration at widest diameter (mm)
    - Tenderness around the wound? (y/n)
    - Removal of packing

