    - Does wound require repacking? (y/n)
- Clinical Options
  - Return to ED for additional clinical evaluation and management (y/n)
      - Reason for reevaluation (infxn worsening/infxn non-improvement/other)
      - Another incision and drainage in the ED (y/n)
      - Addition of oral antibiotics (y/n)
      - Admission for i.v. Abx (y/n)
      - Admission for surgical intervention (y/n)
      - Return to ED in 2 more days (y/n)
- Schedule follow-up visit in Infectious Diseases Clinic at Children's Hospital of The King's Daughters (CHKD) in  $5 \pm 2$  days

Phone Follow up Contact Day Prior to CHKD visit:

Return visit reminder performed by Study Coordinator.

- Fever since leaving ED? (y/n, record temp if taken)
  - If prescribed, has antibiotic been taken (y/n, # doses)
  - If antibiotics taken, were any side-effects noted (y/n, list)
  - Increased or decreased pain (y/n, increased/decreased)
  - Increased or decreased size of redness (y/n, increased/decreased)
  - Any new symptoms? (y/n, list) Specific questions will include: presence of rash, loose stool, nausea, vomiting, abdominal discomfort, headache, dizziness, drowsiness, thrush, as well as any change in local signs or symptoms including pain and redness, new skin lesions, enlarged lymph nodes, and sore or white spots in the mouth.

Visit 3 - Day  $7 \pm 2$ : (CHKD Infectious Diseases Clinic):

Follow up on subjects' wound status. The following information will be collected and recorded on a hard copy Case Report Form at this contact.

- Questions about infection
  - Fever  $> 38^{\circ}\text{C}$  at home since incision? (y/n)
  - Pain (increased/same/decreased/resolved)
  - Redness (increased/same/decreased/resolved)
  - Persistent discharge (y/n)
  - Wound size (increased/same/decreased/resolved)
    - If resolved, day of wound closure (day)
  - New lesions since day 3 visit (y/n)
  - Was an p.o. antibiotic prescribed (y/n)
    - If yes, was the prescription filled (y/n)
    - How many doses have been taken so far? (##)
  - Any diarrhea? (y/n)
  - Any nausea or vomiting? (y/n)
  - Any abdominal discomfort? (y/n)
  - Any new rash? (y/n)

- Any other new symptoms including headache, dizziness, drowsiness, thrush, as well as any change in local symptoms.
- Wound assessment
  - Fever > 38°C in CRU? (y/n, record temp)
  - Packing present (y/n)
  - Diameter of erythema (mm) at widest diameter
  - Diameter of wound (mm) at widest diameter
  - Tenderness around the wound? (y/n)

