- Clinical Assessment (decided by PI or sub-I)
  - Infection worsening, non-improvement, improvement
- Clinical Options (decided by PI or sub-I)
  - No follow-up needed unless infection worsens
  - Suggest follow-up
- Clinical Follow-up, if applicable (obtained from subject or medical record after follow-up)
  - Another incision and drainage in the ED (y/n)
  - Addition of oral antibiotics (y/n)
  - Admission for i.v. Abx (y/n)
  - Admission for surgical intervention (y/n)
  - Return to ED in 2 more days (y/n)

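### Visit 3 and the call before it do not ask every subject about medical evaluation, repeat drainage, ED return or admission since Visit 2

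*Combined protocol and SAP*

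**What the plan says.** The forms are listed under Study Treatments.

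- **Visit 2 (Day 3, window -1/+2)** asks all attendees "Medical evaluation between day 1 and day 3 visit (y/n". Its Clinical Options list then records a return to the ED, another drainage, added oral antibiotics and admission, and includes "Return to ED in 2 more days (y/n".
- **The call on the day before Visit 3** covers fever, antibiotic doses, side effects, pain, redness and new symptoms. It has no item on care received.
- **Visit 3 (Day 7 ± 2)** asks "New lesions since day 3 visit (y/n" and "Was an p.o. antibiotic prescribed (y/n", with follow-on items on whether the prescription was filled and how many doses were taken. It does not ask about medical evaluation since Visit 2. The drainage, antibiotic, admission and ED-return items reappear under "Clinical Follow-up, if applicable (obtained from subject or medical record after follow-up", directly after the investigator chooses between no further follow-up (unless the infection worsens) and suggesting follow-up.
- **Recruitment and Retention** adds: "A medical information release will be obtained from the subject so that outcomes data can be collected related to additional unscheduled visits". No time point, trigger or form is given for requesting those records.

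**The concern.** One interval question, on new lesions, was carried forward from Visit 2 to Visit 3. The question on medical care was not. Yet the plan itself anticipates contacts in that interval: a return two days after a Day 3 visit falls on Day 5.

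Three parts of the plan depend on this information:

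- Risks and Side Effects lists re-accumulation needing a second drainage as a risk of the study packing.
- The Statistical Analysis Plan summarizes infection that persists or worsens.
- The Adverse Reaction paragraph uses the need for a further drainage, because of new fluctuance, to class an event as progression rather than local toxicity.

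The interval also follows removal of the packing at Visit 2, so it is the time after local treatment has ended. If re-drainage is not asked about, a Visit 3 rating of improvement can hide it. The Research Monitor's chart review can use only what the charts contain.

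**Working it through.** The plan states no figure on this point, so the check is a comparison of forms followed by simple arithmetic.

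**1. What each contact asks**

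| Item | Call 1 (Day 2, +2) | Visit 2 | Call before Visit 3 | Visit 3 |
|---|---|---|---|---|
| Medical evaluation in the interval | no | yes, Day 1 to Day 3 | no | no |
| Repeat drainage, admission | no | Clinical Options, recorded at Visit 2 | no | conditional block only |
| ED return | no | Clinical Options, recorded at Visit 2 | no | conditional block only |
| Oral antibiotic | filled, doses | prescribed, filled, doses | doses | prescribed, filled, doses |
| New lesions | in symptom list | yes | in symptom list | yes, since Visit 2 |

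Call 1 normally precedes Visit 2, so only the last two columns bear on the later interval.

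**2. Antibiotics by arm.** The study arm is "Incision + TheraGauze+tobramycin packing (no systemic antibiotics", so a yes to the Visit 3 item there means an antibiotic was added. In controls the prescription at Day 1 is optional. A change from no at Visit 2 to yes at Visit 3 also shows an addition. The item fails only for controls already on an antibiotic, where the Day 1 prescription and a later one look the same.

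**3. Share of follow-up not covered.** Share = (Visit 3 day - Visit 2 day) / (Visit 3 day - 1).

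- Nominal days: (7 - 3)/(7 - 1) = 4/6 = 67%.
- Windows alone (Visit 2 on Days 2 to 5, Visit 3 on Days 5 to 9) give 4 × 5 = 20 combinations. The share runs from 0/4 = 0% (both on Day 5) to 7/8 = 87.5% (Days 2 and 9), and 11 of 20 exceed 50%.
- Visit 2 also schedules the clinic visit 5 ± 2 days later. Requiring a gap of 3 to 7 days leaves 14 combinations. The share runs from 3/7 = 43% (Days 5 and 8) to 87.5%. Of the 14, 11 exceed 50%, 2 equal it and 1 falls below.

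**4. Illustrative event count.** The documents give no rate of re-drainage or other unscheduled care. Assume 5% to 10% of subjects have such an event and half of the events fall between Visits 2 and 3.

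- TheraGauze, all randomized: 100 × 2/3 = 66.7; × 5% to 10% = 3.3 to 6.7; half = 1.7 to 3.3 events.
- TheraGauze, completers only, with equal retention: 50 × 2/3 = 33.3; × 5% to 10% × 1/2 = 0.8 to 1.7 events.
- Both arms together: 100 × 5% to 10% × 1/2 = 2.5 to 5 events among all randomized, or half that (1.25 to 2.5) among 50 completers.

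A Visit 3 question reaches attendees only, so the completer figures apply to the form change. The larger figures need a record check as well.

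**The case against.** The strongest reply is that other routes exist.

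- **Records release.** It is obtained for exactly this purpose.
- **SAE reporting.** Hospitalization is a reportable SAE.
- **Visit 2 Clinical Options.** The drainage and admission items sit under a return to the ED. On one reading of an ambiguous layout, that is where such a return would be written up.
- **The Visit 3 block.** It says only that it is completed if applicable. A reader might infer that it covers solely the subjects whom the investigator selects, but the no-follow-up option makes an exception for worsening, so that is not established.

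These points narrow the gap without closing it. The release has no trigger or defined set of subjects. SAE reporting depends on the site learning of the event, and an outpatient re-drainage need not be an SAE. No instruction says that the Visit 2 list is updated later. None of these routes puts the question to everyone.

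Three stronger inferences are tempting and are not supported:

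- **Added antibiotics are missed in the TheraGauze arm.** They are not, because the Visit 3 prescription item reveals them there.
- **The gap favours TheraGauze.** The drainage and admission question is absent in both arms, and for antibiotics the weaker capture is among controls. The arms are known to the assessors, so differential recording is possible, but nothing in the documents shows its direction.
- **Both phone calls are deficient for this interval.** The first normally comes before it.

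**Conclusion.** The point holds for medical evaluation, repeat drainage, ED return and admission between Visit 2 and Visit 3: no contact asks all subjects about them. For oral antibiotics it holds only for control subjects already on one.

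The uncovered time is 67% of follow-up on the nominal schedule. It is more than half in most schedules that the windows and the 5 ± 2 day rule allow, though not in all. Re-drainage can be under-recorded in either arm. The likely number of events is small, around one or two among TheraGauze completers under the assumed rates, and it would change in proportion to them.

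This is a cheap improvement to data capture in a safety pilot. It does not invalidate the design.

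**What to change.** At the pre-Visit 3 call and at Visit 3, ask every subject whether they have had any medical evaluation since the last study visit (yes/no, date, place). Follow it with the checklist items already on the forms: another drainage, oral antibiotics, admission for intravenous antibiotics, admission for surgery, and ED return. Word the antibiotic item as newly added since the last visit, so that it can be read the same way in both arms.

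Use the release already obtained for one medical-record check on the same fixed day for all randomized subjects in both arms, including those who miss Visit 3. With 50 of 100 expected to complete, that check may be the only source for many subjects.

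The cost is a few form lines and one look-up per subject by the existing coordinators, with no added visit and no change to clinical management. The downside is that the reported failure rate may rise slightly.

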#### **PROTECTION OF HUMAN SUBJECTS:**

This research involves the recruitment, enrollment and management of human subjects participating in research. Adults up to age 65 years at enrollment are being studied because adults commonly suffer skin abscesses. Study oversight by the investigators will assure compliance with all regulatory requirements for Institutional Review Board approval prior to the initiation of the study, and will obtain annual re-approval for study activities.

Potential risks and benefits to subjects and procedures to mitigate risks:

- Physical/Medical
  - Serious Adverse Events will be reported to EVMS IRB
- Confidentiality/PHI
  - All PHI will be maintained in an encrypted and password protected electronic file.

#### **RISKS AND SIDE EFFECTS**

Risks and side effects related to the anti-microbial TheraGauze we are studying include:

- The skin abscess may re-accumulate and require a second drainage procedure and possibly evaluation for deeper infection.
- A new skin abscess may arise while on the study.
- A local allergic or irritation reaction to the wound packing.
- Inadvertent release of PHI

**POTENTIAL BENEFITS.**

There may or may not be direct benefit to subjects. Subjects will receive additional follow-up assessments.

**SUBJECT COMPENSATION.**

Subjects will receive a \$40 gift card to a local merchant at each completed visit.

**ASSESSMENT OF SAFETY**

Subjects must be seen by a physician or an appropriately trained healthcare professional at every study visit, and the evaluation must be documented.

**Adverse Events.** An AE is any untoward medical occurrence in a clinical investigation subject administered a pharmaceutical product and which does not necessarily have to have a causal relationship with this treatment. An AE can therefore be any unfavorable and unintended sign (including an abnormal laboratory finding, for example), symptom, or disease temporally associated with the use of a medicinal product, whether or not considered related to the medicinal product.

**Causality Assessment.** For all AEs, the PI will provide an assessment of causal relationship to the study drug. Causal relationship must be assessed by answering the following question: Is there a reasonable possibility the study drug caused the event?

**Yes:** There is evidence to suggest a causal relationship between the study drug and AE, i.e.: there is a reasonable temporal relationship between the study drug and the event, and the event is unlikely to be attributed to underlying/concurrent disease, other drugs, or other factors.

**No:** There is no evidence to suggest a causal relationship between the study drug and AE, ie: there is no reasonable temporal relationship between the study drug and the event, or the subject did not take the study drug, or the event is likely to be attributed to underlying/concurrent disease, other drugs, or other factors, or the event is commonly occurring in the (study) population independent of drug exposure.

**Adverse Reaction.** An AE assessed as likely having a causal relationship with the intervention (i.e., TheraGauze/tobramycin). Specifically focusing on local-toxicity adverse reactions, we will evaluate for increasing redness, increasing pain or a new rash at the site of the packed wound. Increasing pain or redness could be due to progression of the infection (cellulitis/abscess) or local toxicity or reaction to the tobramycin in the TheraGauze/tobramycin packing. This will be assessed by an Investigator. Increasing purulent drainage or the identification of new areas of fluctuance requiring an additional incision and drainage procedure will be assessed as progression of the infection rather than evidence of local toxicity or reaction to the tobramycin.

**Severity Assessment.** The PI must provide an assessment of the severity of each AE by recording a severity rating, which will be assessed as described below. *Severity*, which is a description of the intensity of manifestation of the AE, is distinct from *seriousness*, which implies a subject outcome or AE-required treatment measure associated with a threat to life or functionality.

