In 2003 Simplex P with tobramycin was the first FDA approved antibiotic impregnated bone cement ([www.stryker.com](http://www.stryker.com)). Preparations of tobramycin-impregnated bone cement appear to generally range from 1g to 1.2g in 20 ml (50 – 60 mg/ml) (Sterling, Crawford et al. 2003, McLaren, McLaren et al. 2008). Tobramycin is reported to be the antibiotic of choice for bone cement for more than 75% of orthopedic surgeons (Fish, Hoffman et al. 1992) with excellent local tobramycin levels and minimal systemic tobramycin levels (Soto-Hall, Saenz et al. 1983, Eckman, Henry et al. 1988, Davies and Harris 1991, Pritchett and Bortel 1992, Brien, Salvati et al. 1993, Sterling, Crawford et al. 2003, McKee, Li-Bland et al. 2010). Despite the extensive literature on tobramycin bone cement there are no mentions of local toxicity. It is notable that so little toxicity has been reported given the significantly varying amounts of tobramycin cement are used for different types of orthopedic procedures and depending on the amount of bone being replaced. The wounds the tobramycin cement are in deep tissue spaces that are highly vascular. In contrast, TheraGauze/tobramycin will be placed into small (2 - 10ml) cutaneous abscesses where the bacterial infection has been walled off to protect the body from spread.

Tobramycin has also been used as a topical ophthalmic preparation for many years both as an ointment and drops (3 mg/ml) (e.g., Tobrex). Despite the very sensitive nature of topical application to the eye the package insert for Tobrex notes <1% hypersensitivity and eye or eyelid irritation is 3%, which is a typical rate for antibiotic eye drops. Additionally, Tobramycin eye drops (3 mg/ml) have been shown to have no adverse effects on reepithelialization and be well tolerated after penetrating keratoplasty (Blavin, Sauer et al. 2012)

Thus, there are several decades of human data demonstrating the safety of tobramycin when used topically for cutaneous and ocular wounds and in surgical wounds. The data suggests that local or systemic toxicity is extremely rare when tobramycin is used in these ways.

**Primary Endpoint.** The primary endpoint of the study is to evaluate the safety of and identify side effects of TheraGauze/tobramycin wound packing compared with standard of care management for cutaneous abscesses requiring incision and drainage.

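### Causality is coded only against the study drug, so control side effects have no investigator code, and the SAP does not name a safety measure that avoids the problem

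*Combined protocol and SAP*

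**What the plan says.** The Primary Endpoint section sets out to "identify side effects of TheraGauze/tobramycin wound packing compared with standard of care management". The Design section says the control arm is there "to provide some data with respect to the side effect profile of current furunculosis management for comparison". Both call for a side-effect profile in each arm.

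The Assessment of Safety section then gives these rules:

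- **Causality Assessment:** "For all AEs, the PI will provide an assessment of causal relationship to the study drug". The answer is No in several cases, among them "or the subject did not take the study drug, or the event is likely to be attributed to underlying/concurrent disease, other drugs".
- **Adverse Reaction:** "An AE assessed as likely having a causal relationship with the intervention (i.e., TheraGauze/tobramycin".

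Both phone scripts (Day 2, and the day before the clinic visit) contain a yes/no side-effect item that applies only to subjects who have taken antibiotics. The study arm is "Incision + TheraGauze+tobramycin packing (no systemic antibiotics", so its subjects reach that item only if an oral antibiotic is added later, which the Visit 2 form allows for. In the control arm an oral antibiotic is optional.

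The same scripts, and Visits 2 and 3, also ask every subject about rash, loose stool or diarrhea, nausea, vomiting, abdominal discomfort and other new symptoms, without asking for a cause.

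The Statistical Analysis Plan promises descriptive summaries of safety and tolerability, and an equivalence test based on a 90% confidence interval. It does not say which safety variable is compared, and it gives no value for the margin.

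**The concern.** The endpoint is worded as a comparison of side effects, but the only investigator judgement that turns an AE into a side effect is defined for one arm. A control with diarrhea from an oral antibiotic, or a skin reaction to an iodoform wick, must be coded No. An analyst who follows the endpoint wording could reasonably take the related-event field as the side-effect variable, and controls would then score zero whatever happened to them. The difference could never favor TheraGauze, although the Background names avoidance of systemic-antibiotic side effects as the main expected benefit.

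The phone item leans the other way. It prompts for side effects almost only in controls, so adding its answers to a between-arm count would raise the control rate through extra questioning alone. There is no reason to expect the two distortions to cancel.

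**Working it through.** **Reading the rules together.** The term study drug is not formally defined. Two things identify it as TheraGauze/tobramycin: the adverse-reaction definition names that product, and the No criteria include not having taken the drug and a likely cause in other drugs. A control meets the first criterion in every case, and antibiotic diarrhea in a control meets the second as well. The nearest exception is the Research Monitor's comment on whether an SAE or death is related to study participation. That is not a regimen code and does not cover ordinary AEs.

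| Event in a control | Investigator code | Other record |
|---|---|---|
| Antibiotic diarrhea | No | symptom items; antibiotic-only phone item |
| Wick or iodoform reaction | No | symptom items only; no attribution |

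**Study size.** 100 randomized × 50% retention = 50 completers, which is the protocol's figure. At 2:1 this gives about 67:33 randomized and 33:17 completing.

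**Side effects coded No.** Diarrhea among antibiotic takers is about 20% (Background). The share of controls given an antibiotic is not stated; I assume 25% to 100%.

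- Rate among all controls: 0.20 × 0.25 = 5%, to 0.20 × 1.00 = 20%.
- Of 33 randomized: 33 × 0.05 = 1.7, to 33 × 0.20 = 6.6.
- Of 17 completers: 17 × 0.05 = 0.9, to 17 × 0.20 = 3.4.

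**Effect on a related-event difference.** For TheraGauze I use the protocol's ophthalmic figure ("eye or eyelid irritation is 3%, which is a typical rate for antibiotic eye drops") as a stand-in. The true difference (TheraGauze minus control) is 3% − 5% = −2 points, to 3% − 20% = −17 points. The coded difference is 3% − 0 = +3 points in every case.

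**Equivalence rule, illustration only.** Inputs are TheraGauze at 3%, a true control rate of 20% (100% antibiotic share), margins of 10 and 15 points (assumed) and exact binomial enumeration. The SAP names no interval method, so two are shown. Each cell is the chance of declaring equivalence with controls coded zero, against the chance with symmetric coding.

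| Arms | Margin | Newcombe | Wald |
|---|---|---|---|
| 67:33 | 10 | 67% vs 0.4% | 86% vs 1.1% |
| 67:33 | 15 | 98% vs 2.2% | 99.6% vs 4.6% |
| 33:17 | 10 | 0 vs 0 | 74% vs 1.7% |
| 33:17 | 15 | 74% vs 1.7% | 92% vs 7.4% |

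At a 25% or 50% share the true difference is −2 or −7 points, inside both margins, so declaring equivalence would be no error. The same holds for −17 points at a 20-point margin.

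**Pooling the antibiotic-only item.** If the extra prompt draws a report from 5% to 20% of takers (assumed), the added control reporters number 33 × 0.25 × 0.05 = 0.4, to 33 × 1.00 × 0.20 = 6.6. That is about 1 to 20 points on the control rate.

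**The case against.** The strongest reply is that the harm needs an analysis nobody has planned. The SAP never names related events or adverse reactions as an outcome. In the text, the adverse-reaction definition serves the Stopping Rules, where limiting it to the test product makes sense. Diarrhea, the event behind all the counts above, is asked in both arms at both calls and both follow-up visits; it is captured and lacks only a causality label. This stands, and it makes the harm conditional.

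The illustration is also open to attack. It sets an eye-irritation rate against diarrhea, assumes no local reactions in controls, and gets its large error rates from 100% antibiotic use and an assumed margin. The 67:33 rows also need all 100 subjects evaluable, when 50 are expected to complete. The zero at 33:17 with a 10-point margin belongs to the Newcombe interval and not to the Wald. All of this stands: these figures show direction and possible size and predict nothing.

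Four stronger readings are tempting, and the documents do not support them:

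- A reader might infer that antibiotic side effects in controls go unrecorded. They are recorded as subject reports through the phone item. What is missing is an investigator code, and any attribution to the wick.
- A reader might infer that nothing can be repaired at analysis. Leaving the antibiotic-only item out, or comparing all-cause AEs, is an analysis choice. Only the investigator attribution never made and the prompt never put to the other subjects are lost.
- The scripts say loose stool and the visits say diarrhea. That differs by contact, not by arm, so it creates no between-arm bias.
- The AE definition ("An AE is any untoward medical occurrence in a clinical investigation subject administered a pharmaceutical product") fits a control with a plain wick and no antibiotic poorly, but nothing in the documents excludes such a subject from AE recording.

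**Conclusion.** The concern holds in a limited form and is worth fixing. Investigator relatedness is defined for one arm only, and the explicit side-effect question reaches almost only the other arm, while the primary endpoint is a side-effect comparison. That conclusion comes from the text. It rests on reading study drug as TheraGauze/tobramycin and on no assumed rate.

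The size depends on the measure used. For all-cause AEs or the shared symptoms, the causality rule causes no bias. For related events, the control rate is understated by 5 to 20 points on diarrhea alone, given the protocol's 20% and an assumed 25% to 100% antibiotic share.

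A reader might go further and infer that the planned primary comparison is itself biased. The documents do not support that, because they never say which safety measure is compared. That silence is why the SAP should choose the unaffected one.

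**What to change.** 1. For analysis only, record for every AE in both arms whether it is related to the assigned regimen, meaning either type of packing and any oral antibiotic. Report this as a secondary measure and label it an open-label judgement. Report TheraGauze/tobramycin adverse reactions within that arm only. Leave the Adverse Reaction definition and the Stopping Rules as they are.
2. Put one treatment side-effect question to every subject at both phone contacts, or keep the antibiotic-only item out of between-arm counts.
3. Add to the SAP: *The between-arm safety comparison is the proportion of subjects with at least one AE of any cause through Visit 3, among all randomized subjects with at least one post-baseline contact. The symptoms asked in both arms are supporting measures. Randomized subjects with no post-baseline contact are shown by arm.*

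The cost is one data field, one line in each phone script and a few SAP sentences. The downsides are some extra unblinded causality judgements, and dilution of the all-cause comparison by background symptoms. The equivalence margin remains undefined and has to be set separately.
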